8.1.2. Repeat and Unscheduled Assessments

For vital sign measurements and 12-lead ECG data only, any predose value recorded in addition to the original value or a postdose value recorded within 15 minutes of the original value will be defined as a repeat value; any postdose value recorded more than 15 minutes after the original value will be defined as an unscheduled value. For all other data types (eg, clinical laboratory values), any value recorded in addition to the original value will be defined as an unscheduled value.

The original scheduled value will be used in all calculations postdose. In the event of any repeats or unscheduled measurements taken pre-dose the values will be considered when determining the baseline value.

Postdose repeats, unscheduled assessments, and ET measurements will be excluded from all calculations with the exception of the baseline derivation (see [Section 8.1.3](#)).

8.1.3. Definitions of Baseline and Change from Baseline

Baseline value is defined as the last non-missing measurement before administration of LOXO-305.

If the date/time of the value is incomplete or missing, it will be excluded from the baseline calculation, unless the incomplete date/time indicates the value was recorded prior to dosing.

Individual changes from baseline will be calculated by subtracting the individual subject's baseline value from the value at the timepoint. The mean change from baseline will be defined as the mean of the individual changes from baseline for all subjects.

See [Section 8.1.2](#) for more detail on handling repeat and unscheduled readings in the calculations.

8.2. Subject Disposition and Population Assignment

Subject disposition and population assignment will be listed.

A summary table by treatment will be provided, based on the all subjects population.

8.3. Demographics and Baseline Characteristics

The demographics and baseline characteristics including age, sex, race, ethnicity, height, body weight, and body mass index will be listed.

A summary table by treatment will be provided, based on the safety population.

8.4. Prior and Concomitant Medication

Prior medication will be defined as medication that ends prior to the dose of LOXO-305. Concomitant medication will be defined as medication that starts during or after dosing LOXO-305 or starts but does not end prior to dosing LOXO-305.

Prior and concomitant medications will be coded using the World Health Organization Drug Dictionary (WHODrug) Global, Format B3, Version March 2020. Prior and concomitant medications will be listed.

8.5. Pharmacokinetic Assessments

8.5.1. Pharmacokinetic Analysis

The following PK parameters will be determined where possible from the plasma concentrations of LOXO-305 using noncompartmental methods in validated software program Phoenix WinNonlin (Certara, Version 8.1 or higher):

Parameter	Units ^a	Definition
AUC _{0-t}	h*ng/mL	area under the concentration-time curve from hour 0 to the last measurable concentration (t _{last}) ^b
AUC _{0-inf}	h*ng/mL	area under the concentration-time curve from hour 0 extrapolated to infinity ^c
AUC ₀₋₂₄	h*ng/mL	area under the concentration-time curve from hour 0 to 24 hours postdose
%AUC _{extrap}	%	percentage extrapolation for AUC _{0-inf}
C _{max}	ng/mL	maximum observed plasma concentration
t _{max}	h	time to maximum observed plasma concentration
λ _Z	1/h	apparent terminal elimination rate constant
t _{1/2}	h	apparent terminal elimination half-life
CL/F	L/h	apparent systemic clearance
V _Z /F	L	apparent volume of distribution during the terminal phase
DAUC _{0-t} ^d	h*ng/mL/mg	AUC _{0-t} normalized by dose administered
DAUC _{0-inf} ^d	h*ng/mL/mg	AUC _{0-inf} normalized by dose administered
AUC ₀₋₂₄ ^d	h*ng/mL/mg	AUC ₀₋₂₄ normalized by dose administered
DC _{max} ^d	ng/mL/mg	C _{max} normalized by dose administered

^a Units are based on concentration units (provided by the bioanalytical lab or preferred units for presentation of PK parameters) and dose units used in the study.

^b Area under the concentration-time curve will be calculated using the linear trapezoidal rule for increasing and decreasing concentrations

^c Based on the last observed quantifiable concentration

^d Calculated by dividing the parameter by the dose (mg)

Additional PK parameters may be determined where appropriate.

PK analysis will be carried out where possible using actual blood sampling times postdose. If an actual time is missing, the sample concentration result will be treated as missing unless there is scientific justification to include the result using the nominal time.

The parameters C_{max} and t_{max} will be obtained directly from the concentration-time profiles. If C_{max} occurs at more than 1 timepoint, t_{max} will be assigned to the first occurrence of C_{max}.

8.5.1.1. Criteria for the Calculation of Apparent Terminal Elimination Rate Constant and Half-life

The start of the terminal elimination phase for each subject will be defined by visual inspection and generally will be the first point at which there is no systematic deviation from the log-linear decline in concentrations.

The apparent terminal elimination rate constant (λ_z) will only be calculated when a reliable estimate can be obtained using at least 3 data points, preferably not including C_{max} , and the adjusted coefficient for determination of exponential fit (R^2 -adj) of the regression line is ≥ 0.7 . Parameters requiring λ_z for their calculation (eg, AUC_{0-inf} , $t_{1/2}$, CL/F , and V_z/F) will only be calculated if the R^2 -adj value of the regression line is ≥ 0.7 .

The following regression-related diagnostic PK parameters will be determined, when possible:

Parameter	Units	Definition
λ_z	1/h	apparent terminal elimination rate constant
λ_z Upper	h	end of exponential fit
λ_z Lower	h	start of exponential fit
λ_z N	NA	number of data points included in the log-linear regression
λ_z Span Ratio	NA	time period over which λ_z was determined as a ratio of $t_{1/2}$
R^2 -adj	NA	adjusted coefficient for determination of exponential fit

Where possible, the span of time used in the determination of λ_z (ie, the difference between λ_z Upper and λ_z Lower) should be ≥ 2 half-lives. If the λ_z Span Ratio is <2 , the robustness of the $t_{1/2}$ values will be discussed in the CSR.

8.5.1.2. Criteria for Calculation and Reporting of Area Under the Concentration-time Curve

The minimum requirement for the calculation of area under the concentration-time curve (AUC) will be the inclusion of at least 3 consecutive concentrations above the lower limit of quantification. If there are only 3 consecutive concentrations, at least 1 should follow C_{max} .

If the extrapolated area is $>30\%$, AUC_{0-inf} (and derived parameters) may be excluded from the summary statistics and statistical analysis at the discretion of the sponsor or pharmacokineticist.

If AUC_{0-inf} cannot be determined reliably for all subjects and/or treatments, an alternative AUC measure, such as AUC to a fixed timepoint or AUC_{0-t} , may be used in the statistical analysis of dose proportionality.

8.5.1.3. Criteria for Handling Below the Limit of Quantification or Missing Concentrations for Pharmacokinetic Analysis

Plasma concentrations below the limit of quantification (BLQ) will be assigned a value of 0 before the first measurable concentration and thereafter BLQs will be treated as missing. The following rules apply with special situations defined below:

- If an entire concentration-time profile is BLQ, it will be excluded from PK analysis.
- Where 2 or more consecutive concentrations are BLQ at the end of a profile, the profile will be deemed to have terminated and any further quantifiable concentrations will be set to missing for the calculation of the PK parameters, unless they are considered to be a true characteristic of the profile of the drug.
- If a predose plasma concentration is missing, it may be set to zero by default within Phoenix WinNonlin.

8.5.1.4. Treatment of Outliers in Pharmacokinetic Analysis

If a value is considered to be anomalous due to being inconsistent with the expected PK profile, it may be appropriate to exclude the value from the PK analysis. However, the exclusion of any data must have strong justification and will be documented in the CSR.

Any quantifiable predose concentration value will be considered anomalous and set to missing for the PK analysis.

8.5.2. Presentation of Pharmacokinetic Data

If the actual time of sample collection deviates from the nominal time by more than $\pm 10\%$, the concentration will be flagged and excluded from the summary statistics. Individual concentrations deemed to be anomalous will be flagged in the listings and excluded from the summary statistics.

For PK concentration data the following rules will apply:

- Values that are BLQ will be set to 0 for the calculation of summary statistics.
- Arithmetic mean or median values that are BLQ will be presented as 0.
- If any BLQ results (treated as 0) are in a series of summarized data, geometric mean and coefficient of variation (CV) of geometric mean will be reported as not calculated (NC).

For PK parameters the following rule will apply:

- Geometric mean and coefficient of variation will not be calculated for t_{max} .

PK analysis will use actual times as recorded on the electronic case report form.

8.5.2.1. Presentation Pharmacokinetic Parameters

For the calculation of summary statistics of PK parameters, all not reported (NR) and Not Calculated (NC) values in a data series will be set to missing.

The AUC values will be set to NC if they have been calculated using fewer than 3 concentrations, and/or 3 concentrations if the last is C_{max} .

8.5.3. Pharmacokinetic Statistical Methodology

All PK concentrations and parameters will be listed.

Summary tables, mean (+ standard deviation [SD]) figures, overlaying individual figures, and individual figures by treatment and time postdose will be provided for plasma PK concentrations. All PK concentration figures will be produced on both linear and semi-logarithmic scales. The +SD bars will only be displayed on the linear scale.

Summary tables by treatment will be provided for all PK parameters, with the exception of diagnostic regression-related PK parameters. Summary statistics (n, Mean, SD, CV, minimum, median, maximum, geometric mean [Geom Mean] and geometric CV [Geom CV]) will be calculated for plasma LOXO-305 PK parameters. Excluded subjects will be listed in the PK parameter tables, but will be excluded from the statistical analysis and summary statistics and noted as such in the tables.

Individual and mean plasma concentration time curves (both linear and log-linear) will be included in the final CSR

8.5.3.1. Statistical Analysis

A statistical analysis will be conducted to investigate the dose proportionality of AUC_{0-24} , AUC_{0-t} , AUC_{0-inf} , and C_{max} .

The natural log (ln) transformed LOXO-305 PK parameters will be analyzed using a power model^{3,4} that can be expressed as a linear regression equation with ln-transformed dose as a covariate:

$$\ln(\text{parameter}) = \text{intercept} + \text{slope} \times \ln(\text{dose}) + \text{random error}$$

For dose proportionality, the slope of the regression line is equal to 1; for dose independence, it is equal to 0.

At first, a statistical linear relationship between the ln-transformed PK parameters and the ln-transformed dose will be verified by including a quadratic ($\ln(\text{transformed dose})^2$) term in the model as indicated above. A 5% level of significance will be used for testing of the quadratic effect. If the quadratic term is not suggested from the model, the slope of $\ln(\text{dose})$ around 1 suggests dose-proportionality from the linear regression model of ln-transformed PK parameters versus $\ln(\text{dose})$.

For each PK parameter separately, an estimate of slope, corresponding 90% confidence interval (CI), and between-subject coefficient of variation (CV) will be calculated from the power model. Figures (on the logarithmic scale) containing individual values, power model line (90% CI), and dose proportionality line (defined as the power model line with slope of 1) will be created for each PK parameter; figures (on the semi-logarithmic scale) containing individual values and geometric means will be created for each corresponding PK parameter normalized by dose administered.

The lack of fit test will be conducted for the statistical assessment of linearity assumption, and thus appropriateness of a power model. The lack of fit model will be the same as the power model fitted, but with dose included as additional fixed effect. The statistical assessment will rule the linearity assumption acceptable if the diagnostic plots appear reasonable and the lack of fit p-value >0.05 (dose effect is not significant at the 0.05 level of significance). The assessment of linearity assumption may also occur via visual examination of the figures by the pharmacokineticist. This assessment may override the statistical assessment; where this occurs, it will be detailed in the CSR.

It will be concluded that PK parameter is dose proportional for the dose range studied if the assumption of linearity is ruled acceptable and the 90% CI for the slope spans 1.

If the assumption of linearity is ruled unacceptable for any PK parameter, its corresponding PK parameter normalized by dose administered will be ln-transformed and analyzed using an analysis of variance (ANOVA) model.⁵ The model will include dose as a factor. For each PK parameter separately, the geometric least squares mean (GLSM) for each dose, p-values for the overall, and pairwise dose comparisons will be calculated.

Residual plots will be produced to assess the adequacy of the model(s) fitted.

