8.3.2. Statistical Methodology

Pharmacokinetic dose proportionality will be assessed for Cohorts 1, 2, and 3. Natural log-transformed AUC_{0-24} , AUC_{0-t} , $AUC_{0-\infty}$, and C_{max} of LOXO-305 will be evaluated using a power model of the form:

$$\ln(\text{parameter}) = \text{intercept} + \text{slope} \times \ln(\text{dose}) + \text{random error}$$

For each PK parameter separately, a pooled estimate (across all doses) of slope, corresponding 95% confidence interval, and between-subject CV% will be calculated.

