1. INTRODUCTION

This SAP has been developed after review of the clinical study protocol (Final Version 1.0 dated 04 August 2020) and electronic case report form.

This SAP describes the planned analysis of the pharmacokinetic (PK), and safety and tolerability data from this study. A detailed description of the planned TFLs to be presented in the clinical study report (CSR) is provided in the accompanying TFL shells document.

In general, the analyses are based on information from the protocol, unless they have been modified by agreement with Loxo Oncology, Inc. A limited amount of information about this study (eg, objectives, study design) is given to help the reader's interpretation. This SAP must be finalized prior to the lock of the clinical database for this study. When the SAP and TFL shells are approved, they will serve as the template for this study's CSR.

This SAP supersedes any statistical considerations identified in the protocol; where considerations are substantially different, they will be so identified. If additional analyses are required to supplement the planned analyses described in this SAP, they may be performed and will be identified accordingly in the CSR. Any substantial deviations from this SAP will be agreed with Loxo Oncology, Inc. and identified in the CSR.

This SAP is written with consideration of the recommendations outlined in the International Conference on Harmonisation (ICH) E9 guideline *Statistical Principles for Clinical Trials* and ICH E3 guideline *Structure and Content of Clinical Study Reports*.^{1,2}

The document history is presented in [Appendix 1](#).

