10. CHANGES FROM THE PROTOCOL-SPECIFIED ANALYSES

Since the finalization of the protocol the dose levels of each cohort have been confirmed as 300 mg, 600 mg, 800 mg, and 900 mg, therefore these values have been included in Section 6 Study Treatments and within the TFL shells.

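### SAP 8.5.3.1 turns failure to reject a slope of 1 into a positive conclusion of dose proportionality, with no limits and no inconclusive outcome

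*SAP*

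**What the plan says.** SAP section 8.5.3.1 fits a power model, regressing ln(parameter) on ln(dose), for AUC0-24, AUC0-t, AUC0-inf and Cmax. For each parameter, "an estimate of slope, corresponding 90% confidence interval (CI), and between-subject coefficient of variation (CV) will be calculated from the power model".

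The section contains two statements about interpretation:

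- A soft one. If a quadratic term in ln(dose) is not needed at the 5% level, a slope "around 1 suggests dose-proportionality from the linear regression model".
- The formal rule. A parameter will be concluded to be "dose proportional for the dose range studied if the assumption of linearity is ruled acceptable and the 90% CI for the slope spans 1".

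Linearity, the first condition of the formal rule, is also passed on non-significance: "The statistical assessment will rule the linearity assumption acceptable if the diagnostic plots appear reasonable and the lack of fit p-value >0.05". The pharmacokineticist may override that assessment by eye. If linearity is rejected, the analysis moves to an ANOVA of dose-normalised values, again without limits.

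Protocol section 8.3.2 plans estimation only: "a pooled estimate (across all doses) of slope, corresponding 95% confidence interval, and between-subject CV% will be calculated". It states no rule for declaring proportionality.

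**The concern.** A confidence interval that contains 1 shows that the data are compatible with proportionality. It does not show that they are incompatible with an important departure from it. Under the SAP rule, every interval containing 1 leads to the same positive statement, whether it is narrow or runs out to a two-fold departure. If the true slope is not 1, a larger variance or a smaller sample raises the chance of that statement.

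Protocol section 3.3 says PK linearity above 300 mg is not known. The study is also meant to inform the choice of dose for a possible QT study (protocol sections 1.4 and 3.2). The SAP is to serve as the template for the study report, so the sentence would carry through. What is at stake is a possibly false statement of proportionality on a secondary objective.

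There is a smaller disclosure point. SAP section 1 promises that "where considerations are substantially different, they will be so identified". Section 10 lists only that "the dose levels of each cohort have been confirmed as 300 mg, 600 mg, 800 mg, and 900 mg". It mentions neither the move from a 95% to a 90% interval nor the added decision rule.

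**Working it through.** The plan gives no power or precision figure to reproduce; the sample size has no formal statistical basis (protocol 8.1, SAP 5).

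**Inputs from the documents.** Doses 300, 600, 800 and 900 mg (SAP 10); six subjects per cohort (SAP 5); 90% interval and lack-of-fit p > 0.05 (SAP 8.5.3.1).

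**Assumptions.** Between-subject CV of 20, 30, 40 or 50%, because the prior-study values are redacted. True slopes of 1.3, 0.7 and 1.5 are illustrative, because no document says what departure matters. All four doses are in the model.

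**Precision of the slope.** The mean of ln(dose) equals ln(600), so the deviations are −0.693, 0, 0.288 and 0.405.

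- Sxx = 6 × (0.4805 + 0 + 0.0828 + 0.1644) = 4.366; df = 24 − 2 = 22; t(0.95) = 1.717.
- SE(slope) = sqrt(ln(1 + CV²) / Sxx); half-width h = 1.717 × SE.
- Example, CV 40%: sqrt(0.1484 / 4.366) = 0.184; h = 0.317.

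**What the rule lets through, with no true slope assumed.** If the residual SD equals the assumed one, any estimated slope up to 1 + h is declared proportional. The dose-normalised ratio, 900 versus 300 mg, is 3^(slope − 1). At that limit the point estimate is 3^h and its upper 90% limit is 3^(2h).

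| CV | SE | h | Largest passing slope | Ratio 3^h | Upper 90% limit |
|---|---|---|---|---|---|
| 20% | 0.095 | 0.163 | 1.16 | 1.20 | 1.43 |
| 30% | 0.140 | 0.241 | 1.24 | 1.30 | 1.70 |
| 40% | 0.184 | 0.317 | 1.32 | 1.42 | 2.01 |
| 50% | 0.226 | 0.388 | 1.39 | 1.53 | 2.35 |

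**How often proportionality is declared.** The interval part comes from the noncentral t distribution. The full rule adds the lack-of-fit F test (2 and 20 df) in 100,000 simulated lognormal trials per scenario.

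| True slope | 900 v 300 mg ratio | Interval contains 1, CV 20/30/40/50% | After lack-of-fit test |
|---|---|---|---|
| 1.0 | 1.00 | 90.0% at every CV | 85.5/85.5/85.5/85.4% |
| 1.3 | 3^0.3 = 1.39 | 7.8/33.6/52.7/63.8% | 7.4/31.9/49.6/60.9% |
| 0.7 | 3^−0.3 = 0.72 | same as 1.3 by symmetry | 7.3/31.9/50.0/60.6% |
| 1.5 | 3^0.5 = 1.73 | 0.0/3.6/16.3/30.9% | 0.0/3.5/15.6/29.5% |

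**Less data makes the claim easier.** At CV 40% and slope 1.3, the interval contains 1 in 71% of trials with 3 subjects per cohort, 65% with 4, 53% with 6, 27% with 12 and 6% with 24.

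**Sensitivity to the cohorts used.** The protocol says "Pharmacokinetic dose proportionality will be assessed for Cohorts 1, 2, and 3". SAP 8.5.3.1 names no cohorts, and the documents do not say which dose each cohort number received. With three doses (df 16, t = 1.746, lack of fit on 1 and 15 df), the rates for slope 1.3 after the lack-of-fit test are:

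- 300/600/900 mg (Sxx 3.704): 12.2/38.4/55.1/64.5%.
- 300/600/800 mg (Sxx 3.050): 17.9/45.3/60.3/67.8%. Here the ratio of highest to lowest dose-normalised exposure is (8/3)^0.3 = 1.34.

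**Interval level.** With a 95% interval and four doses, the interval part at slope 1.3 would pass in 47, 66 and 75% of trials at CV 30, 40 and 50%, against 34, 53 and 64% with 90%. The SAP's choice therefore makes this rule stricter.

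The diagnostic plots and the visual override are not modelled and could move the result either way.

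**The case against.** The strongest reply is that little depends on this sentence. PK is the secondary objective. Escalation rests on PK reviewed after each dose (protocol 3.3 and 5.5), no interim analysis is planned, and the dose levels are already confirmed. Observed Cmax and AUC by dose, which are tabulated, bear more directly on finding a supratherapeutic dose. The report will also show the slope, its interval, the CV and plots against the slope-1 line. The conclusion is confined to the doses studied, and SAP 8.1 advises caution because the sample size is not based on power. All of this stands and holds the severity down. None of it changes the sentence the rule requires.

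A second reply is that the sizes rest on assumed CVs and slopes, and that for slope 1.3 they run from 7% to 68%. That is correct: at CV 20% the problem is small. The flaw in the logic does not depend on the CV; its practical weight does.

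A third is that the preliminary quadratic test is left out of the calculation. The formal rule turns on linearity, which the SAP defines through lack of fit. Treating the quadratic test as a further gate changes little with four doses: about 83% instead of 85% at slope 1, and 7/31/49/59% at slope 1.3. With three doses it coincides with lack of fit.

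Finally, when the true slope is 1, the rule is right about 85% of the time. That is true, but the report's reader does not know the true slope.

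**Conclusion.** The concern holds and should be fixed. The rule makes non-rejection of slope = 1 a positive conclusion, with no limits and no inconclusive outcome in either document. Under the assumed CVs of 20 to 50% and four doses of six subjects, a true slope of 1.3 would be called proportional in about 7 to 61% of trials, and a slope of 1.5 in about 0 to 30%. At CV 40% the report could state proportionality beside an interval that reaches a two-fold departure. The consequence is minor to moderate: one over-strong statement on a secondary objective, with no effect on dosing decisions. Confidence is high on the logic of the rule; the size depends on redacted CVs. The unlisted change in interval level is a disclosure matter only and does not add to the severity.

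**What to change.** In SAP 8.5.3.1, replace the concluding rule with text such as:

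> *If linearity is ruled acceptable, the slope and the implied ratio of dose-normalised exposure at the highest versus the lowest dose in the model will each be reported with a 90% CI. A slope CI that contains 1 means only that the data do not exclude dose proportionality over the doses studied. A slope CI that excludes 1 will be reported as evidence of a departure, with its size given by the ratio.*

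With 300 and 900 mg as the extremes, the ratio is 3^(slope − 1), and its limits come from the slope limits in the same way. Using the highest and lowest doses in the model avoids extrapolation if a dose is left out. The SAP should also state which dose levels enter the model.

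Change the earlier remark about a slope near 1 to match, for example *is consistent with, but does not establish, dose proportionality*. In section 10, list the 90% interval as a change from the 95% in protocol 8.3.2.

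The cost is a few wording changes, one derived ratio per parameter and one line in section 10. No margin, new model or new data is needed. The downside is that the report gives up a yes/no claim. If the true slope is 1, the current rule would state proportionality correctly in about 85% of trials; the revised text would say *not excluded* in those trials, with the same interval.
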